### **13.9. Criteria for End of Study**

This study will be considered complete following the data cut-off date for the final analysis. Documentation of the data cut-off will be included in the master study file. After the final analysis, if subjects are continuing to benefit from study treatment, they will be allowed to continue receiving study treatment for up to one year as part of planned maintenance. Patient is considered “off therapy” when study drug stops for any reason and crenolanib therapy is not continued. Patient is considered “off study” after completion of the 30-day safety follow up, 2 year follow-up period or upon death or upon start of a new therapy, whichever comes first.

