**Planned Duration of Treatment:**

If patients receive all available therapy options, patients may stay on trial for approximately 20 months. Information for survival and disease status (until progression of disease) on patients who have discontinued study drug for any reason should be obtained at least every 6 months for a maximum of 24 months or until the end of the study, whichever is later.

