#### 4. ABBREVIATIONS AND DEFINITIONS

Adverse Event (AE)	Any untoward medical occurrence in a patient or clinical investigation subject administered a pharmaceutical product and which does not necessarily have a causal relationship with this treatment. An adverse event can therefore be any unfavorable and unintended sign (including an abnormal laboratory finding), symptom, or disease temporally occurring during the use of a medicinal (investigational) product, whether or not related to the medicinal (investigational) product.
Audit	A systematic and independent examination of the trial-related activities and documents to determine whether the evaluated trial-related activities were conducted, and the data were recorded, analyzed, and accurately reported according to the protocol, applicable standard operating procedures (SOPs), good clinical practice (GCP), and the applicable regulatory requirement(s).
Compliance	Adherence to all the trial-related requirements, good clinical practice (GCP) requirements, and the applicable regulatory requirements.
Complaint	A complaint is any written, electronic, or oral communication that alleges deficiencies related to the identity, quality, purity, durability, reliability, safety or effectiveness, or performance of a drug or drug delivery system.
Confirmation	A process used to confirm that laboratory test results meet the quality requirements defined by the laboratory generating the data and that AROG is confident that results are accurate. Confirmation will either occur immediately after initial testing or will require that samples be held to be retested at some defined time point, depending on the steps required to obtain confirmed results.
Case Report Form (CRF)	Sometimes referred to as clinical report form: a printed or electronic form for recording study participants' data during a clinical study, as required by the protocol.
Consent	The act of obtaining informed consent for participation in a clinical trial from patients deemed eligible or potentially eligible to participate in the clinical trial. [Patients/Subjects] entered into a trial are those who sign the informed consent document directly or through their legally acceptable representatives.
End of Study (trial)	The date of the last visit or last scheduled procedure shown in the Study Schedule for the last active subject in the study.

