### **7.4. Discontinuations**

#### **7.4.1. Discontinuations of Study Drugs and Disease status/Survival Follow up of Patients**

The criteria for enrollment must be followed explicitly. If a patient who does not meet enrollment criteria is inadvertently enrolled, that patient should be immediately discontinued from the study drug.

Study drug may be held for an extended period of time for comorbidities including but not limited to infections, ICU admissions, severe graft vs host disease, and other comorbidities typically seen in patients undergoing induction, consolidation or allogeneic transplant therapies for AML. Such prolonged drug hold will not require the patient to be taken off study. Study drug can be restarted, even after prolonged drug holds, at the same dose as was last received by the patient. Restart of study drug will require a discussion with the sponsor.

Study drug may be held for an extended period of time if requested by the patient without necessitating the patient to be taken off study. Study drug can be restarted, even after prolonged drug holds, at the same dose as was last received by the patient. Patients will be continued to be followed for survival and disease status per protocol. Safety will be followed as per section 14.

Patients, who for any reason, require treatment with another therapeutic agent for AML or investigational agent will be discontinued from the study drug prior to introduction of the new agent. Restart of study drug will require a discussion with the sponsor.

Patients who have disease refractory to induction or consolidation therapy will be taken off crenolanib but be followed for survival. Similarly, patients who relapse after achieving a response will be taken off crenolanib but be followed for survival.

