#### **Discontinuation due to relapse:**

Patients who have discontinued therapy due to relapse will be followed for safety for 30 days post last dose of crenolanib or until start of another therapy or death, whichever comes first.

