#### **Discontinuation due to toxicity:**

Patients who have discontinued therapy due to toxicities attributable to study drug will be followed for safety for 30 days post last dose of crenolanib or until start of another therapy or death, whichever comes first.

**Long-Term Follow-Up Period:** Only new and ongoing serious adverse events (SAEs) thought to be related to study treatment or protocol procedures should be documented on the CRF and immediately reported to AROG or its designee via the designated transmission method. If drug-related toxicity is present beyond 30 days post-discontinuation, patients must be followed at least for 30 days or until the toxicity resolves.

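### Section 13.9 ends study participation at the start of a new therapy, while 3.2 and 7.4.1 keep the same patients in survival follow-up, and no text says which governs

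*Combined protocol and SAP*

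**What the plan says.** Section 13.9 (Criteria for End of Study) defines when a patient is off study. The status is reached on "completion of the 30-day safety follow up, 2 year follow-up period or upon death or upon start of a new therapy, whichever comes first".

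Two other places set survival follow-up:

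- Section 3.2, Planned Duration of Treatment, asks for "Information for survival and disease status (until progression of disease) on patients who have discontinued study drug for any reason", to be obtained "at least every 6 months for a maximum of 24 months or until the end of the study, whichever is later". It makes no exception for patients who have moved to another treatment.
- Section 7.4.1 covers treatment failure. For primary failures: "Patients who have disease refractory to induction or consolidation therapy will be taken off crenolanib but be followed for survival". For later failures: "patients who relapse after achieving a response will be taken off crenolanib but be followed for survival".

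Section 14.6 uses similar triggers for a narrower purpose. Patients who stop because of relapse "will be followed for safety for 30 days post last dose of crenolanib or until start of another therapy or death, whichever comes first". The rule for stopping because of toxicity has the same form: "Patients who have discontinued therapy due to toxicities attributable to study drug will be followed for safety for 30 days post last dose".

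The end of the study, which is one of the limits in 3.2, is defined in section 4 as "The date of the last visit or last scheduled procedure shown in the Study Schedule for the last active subject in the study". Section 13.9 instead ties completion of the study to the data cut-off for the final analysis.

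Overall survival is a secondary objective (6.2). Section 13.1.1 plans descriptive summaries of time-to-event endpoints by cumulative incidence and Kaplan-Meier methods.

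**The concern.** Refractory and relapsed patients are the ones most likely to need another treatment, and they carry much of the information on overall survival. Section 13.9 closes their participation when that treatment starts. Sections 3.2 and 7.4.1 expect sites to go on recording whether they are alive.

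A site coordinator who works from 13.9 would stop contact; one who works from 7.4.1 would continue. Deaths that a site does not collect cannot be restored later by an analysis rule. If the patients who leave die faster than those still followed, their censoring is informative and the survival curve is too high. If practice differs between sites, the completeness of follow-up differs too.

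**Working it through.** The plan states no figure on this point, so the check is mainly a comparison of texts.

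**1. The rules applied to the same patient**

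| Patient | 13.9 | 3.2 | 7.4.1 |
|---|---|---|---|
| Refractory or relapsed, starts another therapy | Off study at that start, or earlier at 30 days if read literally | Survival information due | Followed for survival |
| Refractory or relapsed, no other therapy | Off study at 30 days if read literally, otherwise at 2 years | Survival information due | Followed for survival |
| Stops for another reason, then starts another therapy | Off study at that start, or earlier at 30 days if read literally | Survival information due, since any reason counts | The sentence on patients who need another agent is silent on survival |

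The first row is a direct conflict between 13.9 and both other sections. In the third row the conflict is with 3.2 alone.

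**2. Can the 2-year period in 13.9 ever operate?** Section 13.9 gives no starting point. I take it as the stop of study drug, because the 24 months in 3.2 concern patients who have stopped. The earliest of 30 days and 2 years is then always 30 days, so on a literal reading the 2-year limb never operates after discontinuation. A lenient reading sets the 30-day limb aside. The rule becomes the earliest of 2 years, death and new therapy, and new therapy still ends participation.

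**3. Does another section settle it?** Section 14.6 confines its triggers to safety. Section 13.9 contains no such limit, speaks of the study as a whole, and puts the 2-year period in the same list. No text ranks the sections or separates off-study status from survival follow-up.

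**4. Is the limit in 3.2 clear?** It is not. It sets a 24-month maximum and then takes the later of that and the end of the study. Whenever the end of the study falls more than 24 months after a patient stops drug, the two parts give different answers. The end of the study itself has the two definitions set out above.

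**5. Direction of the error if 13.9 is followed at new therapy.** At time *t*, let *q* be the share of living patients who have started a new therapy, *h1* their death rate, and *h0* the death rate of all other living patients.

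- True death rate: *q* × *h1* + (1 − *q*) × *h0*
- Rate seen if contact or analysis stops at new therapy: *h0*
- Shortfall: *q* × (*h1* − *h0*)

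The shortfall is positive, and Kaplan-Meier survival too high, wherever *h1* exceeds *h0*. The documents give none of *q*, *h1* or *h0*. If 3.2 and 7.4.1 are followed, these patients stay under observation and no deaths are lost within that window.

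**6. Scale only.** Induction non-responders = 120 × (1 − response rate), with the response rates listed in Table 10:

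- 90%: 120 × 0.10 = 12
- 85%: 120 × 0.15 = 18
- 80%: 120 × 0.20 = 24
- 75%: 120 × 0.25 = 30

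These counts include early deaths, who have no follow-up to lose, and leave out patients who respond and later relapse. They do not count patients who start a new therapy.

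**The case against.** The best defence is that 13.9 only defines a status. It does not say that survival contact stops or that overall survival is censored on that date. Sections 3.2 and 7.4.1 are the operative follow-up rules and agree with each other. The protocol also expects contact after a patient leaves: 14.5 lets follow-up of serious events run past withdrawal, and 14.6 has a long-term follow-up period. The literal 30-day reading makes the 2-year period in 13.9 pointless, which suggests that it was not intended.

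Much of this stands. The intention is very probably that survival follow-up continues, and the literal 30-day reading is the weaker one. But the defence depends on a distinction that 13.9 does not draw, and the new-therapy trigger remains on the lenient reading too. Section 7.4.1 also treats being off study as a status with consequences, since it takes care to say that long drug holds do not bring it about.

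A reader might infer more than the documents support:

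- *That 3.2 ends survival follow-up at progression.* The bracketed limit there follows disease status, and 7.4.1 requires survival follow-up after relapse. That doubt fails.
- *That the protocol prescribes censoring at new therapy, or wrongly omits a censoring rule.* No text prescribes it, and 13.1 leaves analysis detail to a separate SAP. The date cut in 13.8 belongs to the safety analyses.
- *That the bias has a known size.* Simulations gave a 20-month survival estimate between 0.5 and 42 percentage points too high. They assumed induction failure of 10% to 34%, early mortality of 0 or 10.3%, median relapse at 12 to 48 months, median survival after failure of 4 to 18 months, and median time to death in remission of 30 to 120 months. Half or all failures started new therapy after 1 or 3 months, and transplant was ignored. Most of these inputs are not in the documents, and the upward direction follows from assuming a higher death rate after failure. The spread reflects the assumptions and does not size the effect in this trial.

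**Conclusion.** The contradiction is real and should be fixed. As written, 13.9 ends participation at the start of a new therapy for patients whom 3.2 and 7.4.1 keep in survival follow-up, and nothing decides between them. It is probably a drafting carry-over from the safety rule in 14.6.

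The consequence is conditional. No deaths are lost within the 3.2 and 7.4.1 window if those sections are followed. If sites stop at the 13.9 date, deaths after failure are lost, and overall survival is overstated provided that these patients have a higher death rate than those still followed. The number who start a new therapy, and hence the size of the bias, cannot be derived from the documents; the 12 to 30 non-responders only indicate scale. The endpoint affected is secondary and descriptive. The primary response-rate objective does not depend on this rule.

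**What to change.** - **13.9:** state that the 30-day and new-therapy triggers end safety and adverse-event collection only. State separately that a patient is off study for survival at death, withdrawal of consent, or completion of the survival follow-up in 3.2.
- **3.2:** reconcile the 24-month maximum with the later-of rule, so that the length of survival follow-up has one meaning.
- **Section 4 and 13.9:** use one definition of the end of the study.

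The cost is wording in three places. Survival contact at least every six months is already planned in 3.2, so no visit or procedure is added, and no treatment rule changes.

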## 14. SAFETY EVALUATIONS AND APPROPRIATENESS OF MEASUREMENTS

### 14.1. Definitions of Adverse Events

#### 14.1.1. Adverse Event (AE)

Any harm or untoward medical occurrence in a research participant administered a medical product, medical treatment or procedure even if it does not necessarily have a causal relationship with the product, treatment, or procedure. An adverse event can be any unfavorable and unintended sign (including an abnormal laboratory finding, for example), symptom, or disease temporally associated with the use of a medical product, medical treatment, or procedure whether or not considered to be related. All adverse events regardless of grade must be recorded, graded, and reported to the Sponsor.

#### 14.1.2. Serious AE (SAE)

An adverse event that results in any of the following outcomes:

- Death
- Life-threatening adverse event (real risk of dying)
- Hospital admission
- Prolongation of hospitalization
- Persistent or significant disability/incapacity/or change in psychosocial status
- Congenital anomaly
- Requirement of intervention to prevent permanent impairment or damage

### 14.2. Attribution to Study Drug

For reporting purposes, attribution is the assessment of the likelihood that an adverse event is caused by the research agent or protocol intervention. The attribution is assigned by the principal investigator after considering the clinical information, the medical history of the subject, and past experience with the research agent/intervention. This is recorded using one of the following four categories:

- Related
- Possibly Related
- Not Related
- Unknown

Related means that the adverse event was most certainly caused by the procedures involved in the research.

Possibly related means that there is reasonable possibility that the adverse events may have been caused by the procedures involved in the research.

Not related means that the adverse event was due to an underlying disease, disorder, or condition of the subject, or may have been caused by other circumstances unrelated to the research or any underlying disease, disorder, or condition of the subject.

Unknown means that it is unclear whether the adverse event was related to procedures involved in the research, either because more information is needed, and will be provided in follow-up, or because there is no way to make a determination.

An AE is “related or possibly related to the study drug or research procedures” if in the opinion of the principal investigator, it was more likely than not caused by the research procedures. AEs that are solely caused by an underlying disease, disorder or condition of the subject or by other circumstances unrelated to the research or any underlying disease, disorder or condition of the subject are not “related or possibly related”. If there is any question whether or not an AE is related or possibly related, the AE should be reported.

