**13.2.1. Excessive early mortality**

Early stopping rules for excessive mortality will be applied in the safety phase of the study. Early mortality is defined for this study as death due to any cause within 30 and 60 days of the initiation of study treatment. In the VALOR trial, all-cause mortality rates of 7.9% and 19.7% were reported, respectively, for patients with relapsed/refractory AML who received cytarabine and placebo as induction therapy. [14] The 30-day mortality rate of 7.9% from the VALOR trial is similar to the 28-day mortality rate of 10.3% that was reported from a retrospective analysis of more than 3000 patients with newly diagnosed AML, the majority of whom were treated with cytarabine-based regimens as induction therapy.[11]

Based on the above considerations, enrollment in a cohort will be halted if the observed 30- and 60-day early mortality rate exceeds 10% and 20%, respectively, as follows: if 1 or more of the first 6 patients enrolled within a cohort die prior to Day 30 then enrollment of additional patients within that cohort will be halted pending review by the Protocol Safety Committee. Additionally, enrollment will be halted within a cohort if 2 or more of the patients die prior to Day 60. Otherwise, 6 additional patients will be enrolled within the cohort provided none of the other stopping criteria have been met.

For the second group of 6 patients within a cohort, if 2 or more of the patients enrolled within a cohort die prior to Day 30, then enrollment of additional patients will be halted pending review by the Protocol Safety Committee. Similarly, if 3 or more of the patients enrolled within a cohort die

prior to Day 60, then enrollment of additional patients will be halted for that cohort. If these and the other early stopping criteria are not met, then the 12 additional patients will be enrolled within the cohort.

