### **13.2.3. Excessive unexpected crenolanib-related toxicity**

Early stopping rules for excessive unexpected crenolanib-related toxicity will be applied in the safety phase of the study. An unexpected crenolanib-related toxicity is defined as any non-hematologic, adverse event considered related to crenolanib (exclusive of those listed in Section 13.2.2). If the observed rate of unexpected, non-hematologic, crenolanib-related toxicity with CTCAE severity grade 4 exceeds 15% during the first 60 days of treatment then enrollment within a cohort will be halted as follows:

If 1 or more of the first 6 patients enrolled within a cohort experience a CTCAE grade 4, non-hematologic, unexpected crenolanib-related adverse event prior to Day 60 then enrollment of additional patients within that cohort will be halted pending review by the Protocol Safety Committee. Otherwise, 6 additional patients will be enrolled within the cohort provided none of the other stopping criteria have been met. Upon enrollment of the 6 additional patients within a cohort, if 2 or more of the patients enrolled within a cohort experience such an event prior to Day 60, then enrollment of additional patients will be halted pending review by the Protocol Safety Committee. If these and the other early stopping criteria are not met, then 12 additional patients will be enrolled to complete the cohort.

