#### **14.4. Adverse Event Reporting**

AROG has standards for reporting AEs that are to be followed regardless of applicable regulatory requirements that may be less stringent. Lack of drug effect is not an AE in clinical trials, because the purpose of the clinical trial is to establish drug effect.

Adverse Events (AEs) will be evaluated according to CTCAE version 4.03 and documented in medical record. After the Informed Consent Document (ICD) is signed, study site personnel will record the occurrence and nature of each patient's pre-existing conditions, including clinically significant signs and symptoms of the disease. During the study, site personnel will record any change in the pre-existing condition(s) and the occurrence and nature of any new adverse events.

All AEs related to protocol procedures are reported to AROG or designee. All AEs occurring after the patient receives the first dose of study drug must be reported to AROG or its designee via CRF. Investigators will be instructed to report to AROG or its designee their assessment of the potential relatedness of each AE to protocol procedure, studied disease state, study drug, and/or drug delivery system via CRF.

For all AEs, the investigator should specify:

1. ***Seriousness:*** Seriousness of an AE is defined by the criteria described in Section 10.1. A severe AE should not always be considered as serious.
2. ***Date of onset and its duration (start and end dates):*** The investigator should follow up the outcome of any AEs until they return to normal or consolidation of the subject's condition. All adverse events still evolving at the end of the study are to be followed up by the investigator until their resolution or stabilization.
3. ***Severity:*** (using NCI CTCAE v.4.03),

4. **Action taken with respect to study drug:** (no action taken; study drug dosage adjusted/temporarily interrupted; study drug permanently discontinued due to this adverse event; hospitalization/prolonged hospitalization), corrective treatment/therapy given, additional investigations performed
5. **Outcome:** Resolved/Recovered, recovering/resolving, not recovered/resolved, recovered/resolved with sequelae, unknown
6. **Relatedness:** If an AE is related or not related to study drug

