### **14.5. Serious Adverse Event Reporting**

Serious adverse event collection begins after the patient has signed informed consent and has received a tablet or more of study drug. If a patient experiences an SAE after signing informed consent, but prior to receiving study drug, the event will NOT be collected unless the investigator feels the event may have been caused by a protocol procedure.

In case of a SAE, the investigator, within 24 hours of learning of the SAE or subject death, must notify the sponsor (Arog Pharmaceuticals by e-mail: [contact] or [contact]) and transmit the following information (within a signed SAE report form):

- Subject identification code, demographics and vitals
- Description of event with onset and duration (with CTCAE event term & severity)
- Dates, dose and frequency of study drug administered
- Assessment of the seriousness and causality of the event with the study drug using the causality criteria (EVCTM): related versus not related
- Study drug status (dose interrupted or discontinued)
- Date of death (if applicable)
- Concomitant therapy and interventions
- Pertinent laboratory data/diagnostic tests
- Pertinent medical history including underlying diagnosis

All SAEs must be followed by the investigator until resolution or stabilization until the subject's death. This may mean that follow-up will be extended beyond the subject's withdrawal from the trial. The investigator must provide follow-up information (outcome, more precise medical details, results of investigations, copy of discharge summary, etc...) within 24 hours of information becoming available to Arog Pharmaceuticals and to the study monitor, again using the SAE Report Form indicating follow-up. When this information is passed on, care must be taken to continue to respect subject anonymity. The study monitor may contact, or visit the investigator, in order to obtain details of the event.

The sponsor will report all SUSAR to the country specific regulatory authorities within the request period. The evaluation of expectedness is based on knowledge of the adverse reaction on the reference document: the current reference document is the latest version of the Investigator's Brochure of crenolanib.

The sponsor will also inform the IRB of any SAE with the potential to modify the benefit/risk ratio of the present study. The sponsor will be responsible for reporting of New Safety Issues and Annual Safety Reports to IRBs.

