#### **14.8. Deaths**

All deaths that occur during the study should be reported as follows:

- Death, which is unequivocally due to disease progression, should be communicated to the study monitor at the next monitoring visit and should be documented in the CRF module, but should not be reported as a SAE during the study
- Where death is not clearly due to disease progression of the disease under study the AE causing the death should be reported to the study monitor as an SAE within 24 hours of becoming aware of the event. The report should contain a comment regarding the co-

involvement of progression of disease, if appropriate, and should assign a single primary cause of death together with any contributory causes

- Deaths with an unknown cause should always be reported as a SAE (within 24 hours of becoming aware of the event) but every effort should be made to establish a cause of death. A post-mortem may be helpful in the assessment of the cause of death, and if performed, a copy of the post-mortem results (with translation of important parts into English) should be reported in an expedited fashion to the sponsor within the usual timeframes

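### Section 14.2 sets two different tests for relatedness and the Grade 4 halting counts do not say which applies, so one event can halt a cohort or not; a separate conflict over death reporting can delay a halt

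*Combined protocol and SAP*

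**What the plan says.** **Relatedness.** Section 14.2 has four categories: *related*, *possibly related*, *not related* and *unknown*. It describes *possibly related* as meaning that "there is reasonable possibility that the adverse events may have been caused by the procedures involved in the research". The closing paragraph of the same section puts an event in the combined class of related or possibly related if the principal investigator thinks "it was more likely than not caused by the research procedures". It then rules out events caused solely by the underlying disease or by other unrelated circumstances, and asks that doubtful cases be reported.

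The forms are coarser. Section 14.4 asks the investigator to state "If an AE is related or not related to study drug", and the SAE report in 14.5 is also two-way.

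**Halting counts.** Section 13.2.3 covers unexpected toxicity, "defined as any non-hematologic, adverse event considered related to crenolanib" and not already listed in 13.2.2. At Grade 4 before Day 60, 1 of the first 6 patients or 2 of 12 halts enrolment in that cohort pending committee review. Section 13.2.2 uses 2 of 6, then 3 of 12, for expected crenolanib-related Grade 4 events. Neither section refers to 14.2.

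**Deaths.** Section 13.2.1 counts "death due to any cause within 30 and 60 days of the initiation of study treatment", and one death before Day 30 among the first six halts the cohort. Section 14.5 says that the investigator, "within 24 hours of learning of the SAE or subject death, must notify the sponsor". Section 14.8 says that a death beyond doubt due to progression "should be communicated to the study monitor at the next monitoring visit" and is not an SAE.

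**The concern.** A halting rule works only if everyone who feeds it counts the same events. Here two sites could follow different sentences of 14.2 in good faith and classify the same Grade 4 event differently. With thresholds of one or two patients, one classification can settle whether the committee is called in at all. The problem is sharpest for toxicities that the chemotherapy also causes. Section 13.2.2 itself anticipates the listed toxicities, or similar ones, at relatively higher frequency with the chemotherapy, so many events could plausibly be due to crenolanib without crenolanib being the likelier cause. The looser the test, the more often the rule protects; the stricter the test, the more often enrolment continues.

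The death conflict is of a different kind. If a site follows 14.8, the sponsor may learn of a countable death only at a later monitoring visit, and patients may be enrolled in the meantime.

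**Working it through.** **1. The plan's own counts.** For each rule, take the smallest count whose share of patients exceeds the stated rate, with the second look cumulative over 12 patients.

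| Rule | Rate to exceed | First 6 | All 12 |
|---|---|---|---|
| Deaths by Day 30 | 10% | 1/6 = 16.7% | 2/12 = 16.7% (1/12 = 8.3%, no halt) |
| Deaths by Day 60 | 20% | 2/6 = 33.3% | 3/12 = 25.0% (2/12 = 16.7%, no halt) |
| Expected Grade 4 | 20% | 2/6 = 33.3% | 3/12 = 25.0% |
| Unexpected Grade 4 | 15% | 1/6 = 16.7% | 2/12 = 16.7% |

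All eight counts in 13.2.1 to 13.2.3 are reproduced. Applying the second look to the second six patients alone would give 1, 2 and 1 for the 10%, 20% and 15% rates instead of the stated 2, 3 and 2, so the second look is cumulative.

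**2. One patient.** Suppose one of the first six has an unexpected Grade 4 event for which crenolanib is a reasonable possibility but not the likelier cause. By the category definition the count is 1/6 = 16.7%, above 15%: halt. By the closing paragraph's test it is 0/6: continue.

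**3. Chance of halting by 12 patients.** The documents give neither the true Grade 4 rate nor the share *f* of reasonably possible events that also meet the stricter test, so both are assumed. Take a reasonable-possibility rate of 10% or 20% of patients and *f* of 1, 0.5 or 0.25. The counted rate is p = rate × *f*. Patients are taken as independent, and each rule is looked at alone in one cohort.

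With X the number of events in a group of six:

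- 13.2.3: P(halt) = P(X ≥ 1) + P(X = 0) × P(X ≥ 2)
- 13.2.2: P(halt) = P(X ≥ 2) + P(X = 0) × P(X ≥ 3) + P(X = 1) × P(X ≥ 2)

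For 13.2.3 at p = 0.10: P(X = 0) = 0.9^6 = 0.5314 and P(X ≥ 2) = 0.1143, so P(halt) = 0.4686 + 0.5314 × 0.1143 = 0.529. At p = 0.025 (10% with *f* = 0.25): 0.1409 + 0.8591 × 0.0088 = 0.148.

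| Reasonable-possibility rate | *f* | Counted rate p | 13.2.3 halts | 13.2.2 halts |
|---|---|---|---|---|
| 10% | 1 | 10% | 52.9% | 16.3% |
| 10% | 0.5 | 5% | 28.9% | 4.2% |
| 10% | 0.25 | 2.5% | 14.8% | 1.0% |
| 20% | 1 | 20% | 82.8% | 50.6% |
| 20% | 0.5 | 10% | 52.9% | 16.3% |
| 20% | 0.25 | 5% | 28.9% | 4.2% |

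The *f* = 1 rows are the looser test. The other rows are what remains under the stricter one.

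**4. Deaths.** The rule in 13.2.1 is all-cause, so a progression death adds one to the count whether it is notified in 24 hours or at the next visit. The count does not change; the date on which it is known does. The interval between monitoring visits is not stated, so the delay cannot be calculated.

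**The case against.** The best defence of 14.2 is that its closing paragraph says *if*, not *only if*. The next sentence excludes only events due solely to other causes, and the one after leans towards reporting. Read as a whole, the section is loosely drafted and inclusive. This stands as far as it goes: a reader might infer that the plan imposes a bar above 50%, and the text does not firmly say so. But it does not settle the count. The sentence on doubtful cases governs reporting, and all adverse events after the first dose are reported anyway under 14.4. An event with mixed causes lies between the stricter test and the exclusion of solely unrelated events, and *unknown* is on neither side.

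There are also other safeguards. The sponsor monitors events continuously, the committee reviews safety periodically (13.2), and data meetings are held at least every six months or for every 6 patients per cohort (15.2). A Grade 4 event called unrelated therefore remains visible. This reduces the harm, but the counts exist so that a halt does not wait on judgement.

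A reader might infer that the primary safety objective depends on attribution. It does not: the summaries in 13.8 cover adverse events whatever their attributed cause. Only the two toxicity counts are affected.

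On deaths, a reader might infer that the conflict decides whether a cohort halts. The all-cause definition excludes that. Section 14.8 defers only deaths that are beyond doubt due to progression; unclear or unknown causes still go in within 24 hours. It can be read as an exception to 14.5, which excludes progression events from SAE reporting and opens its 24-hour sentence with the case of an SAE. Yet that sentence names subject death separately and without an exception. Twice-monthly calls (15.2) and the limit of 3 of the first six patients within 30 days of starting induction (13.2) shorten or contain a delay, but no text requires deaths to be reported on those calls.

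**Conclusion.** The point holds in two parts of unequal weight. The relatedness wording can change **whether** a cohort halts: a single patient is enough under 13.2.3. Under the assumed rates, the chance of halting by 12 patients falls from 53% to 15–29% (10% reasonably possible) or from 83% to 29–53% (20%). For the expected-toxicity rule the falls are from 16% to 1–4% and from 51% to 4–16%. These figures show sensitivity; they are not estimates. The protocol's only cue, that Grade 4 made up under 5% of reported cases in single-agent studies (13.2.2), is a share of cases rather than of patients, and it fixes neither the rate nor *f*.

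The death-reporting conflict can change only **when** a cohort halts, by an interval that the documents do not allow one to compute. Both parts should be corrected, because they bear on the safety-phase monitoring of each cohort.

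**What to change.** - **14.2:** keep one standard, by replacing the sentence containing the stricter test with the reasonable-possibility definition already given there.
- **13.2.2 and 13.2.3:** state that *related* and *possibly related* events count, and that the Protocol Safety Committee classifies *unknown* events. Counting every *unknown* automatically would bring chemotherapy toxicity into a crenolanib rule; ignoring them would lose unresolved cases.
- **14.4 and 14.5:** make the relatedness fields match the 14.2 categories.
- **14.5 and 14.8:** reconcile them so that every safety-phase death through Day 60, whatever its cause, reaches the sponsor within the 24 hours that 14.5 already states, for the 13.2.1 count, without having to be classed as an SAE.

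The cost is wording, a small change to the CRF and SAE form, and possibly more pauses for committee review. The form change is needed: a reader might assume that the data are already in hand, but a two-way field cannot identify *possibly related* or *unknown* events afterwards.
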